Figure 2: Map of TRiAD Clinical Research Sites in South Africa, Nigeria and Ethiopia.....	30
Figure 3: Study screening and enrolment for the TRiAD Study	33

ABBREVIATIONS AND ACRONYMS

AE	Adverse Events
ADR	Adverse Drug Reaction
AFB	Acid-fast bacilli
AIDS	Acquired Immunodeficiency Syndrome
AIGHD	Amsterdam Institute For Global Health And Development
ART	Antiretroviral Treatment
BDQ	Bedaquiline
BMI	Body Mass Index
BPaL	Bedaquiline-Pretomanid-Linezolid
BPaMz	Bedaquiline-Pretomanid-Moxifloxacin-Pyrazinamide
BREC	Biomedical Research Ethics
CAPRISA	Centre For The AIDS Programme Of Research In South Africa
CFZ	Clofazimine
Co – PI	Co - Principal Investigator
CRF	Case Report Form
CRS	Clinical Research Site
CT	Cycle Threshold
DAIDS	Division of Acquired Immunodeficiency Syndrome
DALY	Disability Adjusted Life Year
DLM	Delamanid
DNA	Deoxyribonucleic Acid
DR-TB	Drug-Resistant TB
DSMB	Data Safety Monitoring Board
DST	Drug Susceptibility Testing
DS-TB	Drug-Sensitive TB
E	Ethambutol
eCFU/ml	Estimated Colony Forming Units Per Millilitre
eCRF	Electronic Case Report Form
EDC	Electronic Data Capture
EDCTP	The European And Developing Countries Clinical Trials Partnership
EDR	Electronic Drug Resistant Software
EPHI	Ethiopian Public Health Institute
FDA	Food And Drug Administration
FIND	The Foundation For Innovative New Diagnostics
FQ	Fluoroquinolones
GCDMP	Good Clinical Data Management Processes
GCP	Good Clinical Practice
HIV	Human Immunodeficiency Virus
HREC	Human Research Ethics Committee
HR-TB	TB resistant to INH with no resistance to rifampicin
IATA	International Air Transport Association

ICF	Informed Consent Form
IHVN	Institute Of Human Virology Nigeria
INHhd	High-Dose Isoniazid
IRB/IEC	Institutional Review Board/Independent Ethics Committee
JSC	Joint Steering Committee
KNCV	KNCV Tuberculosis Foundation
KZN	KwaZulu – Natal
LFX	Levofloxacin
LPA	Line Probe Assay
LTBI	Latent TB Infection
LTFU	Loss To Follow-Up
LZD	Linezolid
TB-MBLA	Tuberculosis - Molecular Bacterial Load Assay
MDR-TB	Multi Drug-Resistant TB
MGIT	Mycobacteria Growth Indicator Tube
MIC	Minimum Inhibitory Concentration
MMT	Medical Monitoring Team
M.tb	Mycobacterium Tuberculosis
MXF	Moxifloxacin
NGS	Next-Generation Sequencing
NHREC	National Health Research Ethics Committee
NIMR	National Institute For Medical Research
NTP	National Tuberculosis Control Programme
OCR	optical character recognition
OSR	Ospedale San Raffaele
PDST	Phenotypic Drug susceptibility testing
PTB	Pulmonary TB
PI	Principal Investigator
PID	Participant's ID
PLWHA	People Living With HIV/AIDS
PTO	Prothionamide
QA	Quality Assurance
QC	Quality Control
QTc	Quantum Tunnelling Composite
RNA	Ribonucleic Acid
rRNA	Ribosomal RNA
RR-TB	Rifampicin-Resistant TB
RT-qPCR	Reverse Transcription quantitative PCR
SA	South Africa
SA DoH	South African Department Of Health
SA GCP	South African Good Clinical Practice
SAE	Serious Adverse Events
SAPHRA	South African Health Products Regulatory Agency
SAS	Statistical Analysis Software

SERO	Scientific And Ethical Review Office
SOC	Standard Of Care
SoE	Schedule Of Events
SOP	Standard Operating Procedure
STREAM	Short Standardized Regimen For The Treatment Of Rifampicin-Resistant Tuberculosis: A Randomized Non-Inferiority Trial To Evaluate A Short Standardized Regimen For The Treatment Of Rifampicin-Resistant Tuberculosis
STR	Shorter Treatment Regimen
TB	Tuberculosis
TRD	Terizidone
TTT	Time to positivity
TRiAD	Triage Test For All Oral DR-TB Regimen
USTA	University Of St Andrews
WGS	Whole Genome Sequencing
WHO	World Health Organisation
XDR-TB	Extensively Drug-Resistant TB
Z	Pyrazinamide

1. STUDY SUMMARY

The TRiAD study is a multi-center, multi-country Prospective Pragmatic Cohort study assessing the effectiveness, feasibility, acceptability, and cost-effectiveness of implementing the Xpert MTB/XDR (Xpert XDR; Cepheid) assay for rapid triage-and-treatment with short, all-oral drug resistant tuberculosis (DR-TB) treatment. The proposed study aims to screen approximately 4800 GeneXpert MTB/RIF or Ultra MTB-positive participants or any currently available Nucleic Acid Amplification Tests for drug-resistance detection changes (irrespective of rifampicin resistance status) from clinical research sites in South Africa, Nigeria and Ethiopia to enrol 880 rifampicin resistant (RR) and 400 rifampicin sensitive and isoniazid, fluroquinolone and or second line injectable drug (SLID) resistant participants over a period of 12-18 months. The Xpert XDR assay, a rapid genotypic test, will be implemented as a reflex test to detect resistance to isoniazid, fluoroquinolones and second-line injectable agents to provide rapid genotypic susceptibility testing for DR-TB detection. Participants that test positive for *Mycobacterium tuberculosis* (*M.tb*) with rifampicin resistance will be enrolled in *Cohort 1* (n=880). Participants that test positive for *M.tb* that are rifampicin susceptible with isoniazid, fluroquinolone and or second line injectable drug (SLID) resistant will be enrolled in *Cohort 2* (n=400). Results from the Xpert XDR assay will be used to guide selection of appropriate, evidence-based, all-oral DR-TB treatment regimens of shortest possible duration. The tuberculosis molecular bacterial load assay (TB-MBLA) will be used as an adjunct to provide bacillary load monitoring over the course of treatment to assess real-time treatment response. Operational research will provide information about the feasibility, acceptability and cost-effectiveness to inform policies and guidelines for programmatic implementation of the triage-and-treat model.

[figure not shown]
Table 1 Overview of TRiAD Study

Study Aim	To evaluate the effectiveness, operational feasibility, acceptability, and cost-effectiveness of implementing the Xpert MTB/XDR assay for rapid triage and selection of all-oral regimens for Drug-Resistant Tuberculosis (DR-TB)
Study Design	Prospective Pragmatic Cohort Study: non-randomized interventional phase 4 (clinical access protocol) implementation science study utilizing interventions of proven clinical efficacy
Study Duration	48 months: study enrolment will occur over 12 -18 months
Sample Size	A total of 1280 participants will be enrolled between 2 prospective study cohorts: Cohort 1 (newly diagnosed DR; rifampicin resistance [RR-TB] participants; n=880) and Cohort 2 (rifampicin sensitive and isoniazid, fluroquinolone and or second line injectable drug (SLID) resistant participants; HR-TB; n=400). Data from a historical cohort (Cohort 3; n=220) of RR-TB participants that accessed DR-TB care at each implementing site over the last 2 years (approximately 24 months) prior to study start.

Study sites	South Africa (n=2), Nigeria (n=6) and Ethiopia (n=5)
Study population	Adult participants (18 years and over) who test positive for pulmonary M.tb with HR-TB or RR-TB will be approached for study participation
Study intervention	Xpert MTB/XDR assay as a triage test to guide early initiation of an appropriate all-oral DR-TB treatment regimen
Study Objectives	
Primary Objectives:
 
 • To compare the time to initiation of resistance-pattern appropriate TB treatment from the date of first sputum collection with the standard of care compared to a historical cohort, stratified by geographical location • To assess the proportion of DR-TB participants with cure and/or DR-TB treatment completion at month 12 compared to a historical control group 
Secondary Objectives:
 
Clinical:
 
 • To assess the safety and effectiveness of all-oral regimens under operational conditions • To assess all-cause mortality at month 12 and 18, rates of drug-related discontinuation for safety concerns and rates of drug-related adverse events 
Microbiological:
 
 • To assess time to culture conversion, cure, and rates of clinical TB relapse • To determine the prevalence of HR-TB stratified by geographic location • To determine the prevalence of pre-XDR and XDR-TB using phenotypic DST to bedaquiline, pretomanid and linezolid • To determine the proportion of participants with bedaquiline and linezolid resistance warranting a switch from short-course treatment • To assess the clinical utility of the TB Molecular Bacterial Load Assay (TB-MBLA) as a predictor of treatment outcome • To assess the diagnostic and clinical performance of the test and triage approach by geographic location using whole genome sequencing (WGS) and Minimum Inhibitory Concentration (MIC) analysis • To determine the phylogenetic structure and full drug resistance patterns of study samples, including bedaquiline, linezolid, levofloxacin and pretomanid

Cost-effectiveness, feasibility and acceptability compared to the standard of care:

- To determine cost per person tested and incremental cost per DR-TB participant timely initiated on the resistance-pattern appropriate regimen
- To determine the incremental cost per Disability Adjusted Life Year (DALY) averted and per day delay averted in treatment with the resistance- pattern appropriate regimen
- To assess programmatic cost-effectiveness, feasibility, and acceptability of implementing any currently available Nucleic Acid Amplification Tests for drug-resistance detection changes with Xpert MTB/XDR testing for HR and second-line DR-TB drugs
- To investigate participant's, health care provider's and policy-maker's acceptability of the triage and treat approach
- To assess the feasibility of the implementation of the triage and treat approach in routine care

¹ All currently available Nucleic Acid Amplification Tests for drug-resistance detection Positive sputum samples will be screened using Xpert XDR assay until we meet the recruitment target for cohort 2. Thereafter, only RR-TB patients will be screened for cohort 1. Xpert XDR detects resistance to INH, Fluoroquinolones and 2nd Line Injectables

² All eligible patients will provide an additional sputum sample for Xpert XDR testing at screening, if reflex testing on provided sputum sample is not feasible

³ Phenotypic DST to BDQ, Linezolid and Clofazimine will be offered for pre-XDR TB cases as per in-country guidelines

⁴ Choice of regimen will be guided by best available evidence from clinical trials using novel regimen, current WHO and in-country guidelines as described in Table 2

⁵ Primary outcome measures for cohort 1 will be compared to a historical dataset of DR-TB patients diagnosed and treated at the each of the facilities over the last 2 years (approximately 24 months)

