through a multi-step testing cascade. Currently, the front-line molecular diagnostic assay for drug resistance is Cepheid Xpert MTB/RIF or Xpert MTB/Ultra, which detects the presence of *M.tb* bacilli and simultaneously detects RR-TB. Whilst rapidly identifying patients eligible for MDR-TB treatment, the test is limited to the detection of RR only (7, 8). Patients who display RIF resistance receive reflex testing which includes resistance to fluoroquinolones and second-line injectables using standard phenotypic drug susceptibility testing (pDST) and the Hain Line Probe Assays (LPA 1 and 2), which detect resistance to isoniazid, rifampicin, fluoroquinolones and second-line injectable agents (9). Drug susceptibility testing (DST) for all other drugs is conducted using phenotypic testing methods. However, following a rapid diagnosis by Xpert MTB/RIF or Xpert MTB/Ultra, all follow-on testing is conducted at a regional laboratory thereby increasing the turn-around times for providing a comprehensive resistance profile. Furthermore, these DST methods have several limitations. Although LPA testing can be rapidly performed on sputum samples, LPAs require specialised laboratory facilities, longer turnaround time and are associated with a high indeterminate rate (~30%) in smear-negative patients (10). Phenotypic DST (pDST) techniques require approximately 4-6 weeks and result interpretation are compounded by issues with the established critical drug concentrations used to predict resistance and poor performance for certain drugs such as ethionamide and pyrazinamide. Currently, DR-TB patients are initiated on empiric treatment, which is modified as DST results become available, resulting in a 4-6-week delay in initiation of appropriate treatment. As a result of this sub-optimal testing cascade, many patients may receive a limited number of effective drugs in the regimen, increasing the risk of amplifying drug resistance and ongoing transmission of DR-TB (3). A further challenge which hinders the diagnosis and treatment of DR-TB is the lack of susceptibility testing for isoniazid resistance by assays available at the point where the patient enters the care cascade, i.e. Xpert MTB/RIF, Xpert MTB/RIF Ultra, or the Truenat assays. As a consequence, isoniazid mono-resistant TB patients (HR-TB; i.e. patients who display INH resistance in the absence of RIF resistance) are not appropriately diagnosed. This sub-set of patients receive standard DS-TB treatment, thereby increasing the risk of amplifying drug resistance (11).

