5. STUDY INTERVENTION

There are 3 study interventions:

1. The Xpert MTB/XDR assay will be used as a diagnostic adjunct to any currently available Nucleic Acid Amplification Tests for drug-resistance detection changes to screen participants. The Xpert MTB/XDR assay will enable prompt identification of the following DR-TB participant categories:
 - a. HR-TB
 - b. Rif mono-resistant TB
 - c. MDR-TB
 - d. Additional fluoroquinolone (FQ) resistance, i.e., pre- XDR TB
2. Early initiation of the most appropriate, evidence-based DR-TB regimen. This will be guided by the TB resistance pattern categorization from the Xpert MTB/XDR diagnostic.

Choice of DR- TB regimen will be determined by:

- a. Best available evidence generated from use of novel regimens as they become available, or
 - b. Current WHO and in-country guidelines (Table 2).
3. In parallel, the TB-MBLA will be used to provide real-time bacillary load monitoring over the course of treatment to assess response to treatment.

Table 2: Current Drug-Resistant TB Treatment Regimen by TB resistance profile and proposed study approach

Current Guidelines on DR- TB treatment	Regimen class	Current Recommended Regimen with Duration (months) by Drug resistance profile per participating country	Proposed All-oral regimen [#]
	HR-TB	RHZE + Lfx (6)	RHZE + Lfx (6) [#]
RR-TB and MDR-TB Short- Course Regimen		
All oral regimen:
 
SA: (4-6)BDQ-Lfx (or MXF)- LZD, INHhd-CFZ-E-Z/ (5) LFX-CFZ-E-Z Nigeria: (4-6)BDQ-MFX-HH-PTO-CFZ-E-Z/ (5)BDQ (2) MFX-CFZ-E-Z Ethiopia:(4-6)AM-MFX-CFZ-HH-PTO-E-Z/ (5)MFX-CFZ-E-Z
 
or
 
Injection-based regimen:
 
(4)AMK-MFX-CFZ- INHhd -PTO-E-Z/(5) MFX-CFZ-E-Z
	BDQ based all-oral regimen [#]
RR-TB; MDR-TB; and PreXDR-TB (Second-line resistance) Long all-oral Regimen* :		
SA: (6)BDQ-LFX-CFZ-LZD/(12)LFX-CFZ- LZD Nigeria: (6)BDQ-MFX-CFZ-LZD/ (12) MFX- CFZ-LZD Ethiopia: (6) BDQ-LFX-LZD-CFZ-CS/(14) LFX- LZD-CFZ-CS
	BPaL [#]
PreXDR-TB (FQ resistance) and XDR-TB# Long Individualised Regimen*:		
SA: (6-8)BDQ-CFZ-LZD-DLM-TRD/(12)CFZ-LZD-TRD-Z- INHhd Nigeria: (6)BDQ-CFZ-LZD-CS/ (12)CFZ-LZD- CS Ethiopia: (BDQ)-(LFX)- (MFX)-(LZD)-(CFZ)-(CS)- (DLM)-(PTO)-(Z)-(AM)-(S)-(PAS)
	BPaL [#]

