6.2.3. Selection of Historical Cohorts

Each CRS will build a dataset of historical RR-TB participants that were diagnosed and started on treatment within 12 - 18 months prior to starting enrolment of the study at each of the clinical research sites. Clinical and laboratory data from this retrospective cohort will be obtained from treatment registers, participant charts and laboratory databases at each of the clinical research sites. The following data variables will be extracted: date of birth, or age, sex, HIV and ART status, facility or clinic, year and month of treatment, type of DR-TB, certainty of diagnosis (confirmed by DST or presumed, i.e., contact of DR-TB source case or failing adherent first-line TB treatment), disease classification, treatment start date and any bacteriological results on treatment (date, mycobacterial culture, DST and genotypic results), where relevant. Data on all drugs from previous DR-TB treatment regimen, DR-TB Outcomes: cure, completion, default, death, loss to follow up (LTFU) will be abstracted. Historical data will be collected on specially designed case report forms (CRF) and will be subject to routine quality assurance/control QA/QC of data to ensure maximum quality. Bias by time period and by other confounders such as HIV, gender and age, will be controlled for in the analysis. No historical data will be generated for cohort 2, as no routine data on HR-TB is available.

6.3. Participant Inclusion Criteria for cohorts 1 and 2

1. Ambulant adults \geq 18 years of age
2. Newly diagnosed PTB patients receiving less than 5 days of treatment since new diagnosis:
 - a) Cohort 1: < 5 days of DR-TB treatment
 - b) Cohort 2: < 5 days of INH mono-resistant TB treatment preceding study entry for the current TB episode, or
3. Sputum positive (smear and or culture) TB patients classified as failing first line treatment
4. Any currently available Nucleic Acid Amplification Tests for drug-resistance detection changes/assay positive for M.tb infection with:
Cohort 1: at least Rifampicin resistance

- Cohort 2: Rifampicin susceptible co-occurring with INH, fluoroquinolone, ethionamide or aminoglycoside resistance (detected by Xpert XDR) occurring alone or in combination
5. Capacity to provide informed consent
 6. HIV infected and uninfected participants are allowed in the study. Participants already on ART will be allowed in the study provided the ART regimen in use has no contraindications to the proposed TB drug regimen

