²TB-MBLA testing: the test will be conducted on stored sputum samples. The test will be conducted using LifeArc TB-MBLA test kits. This assay will be conducted to assess the clinical utility of the assay, not for clinical management. It is a reverse transcription quantitative polymerase chain reaction (RT-qPCR) assay that uses 16S-rRNA as a marker to detect and quantify the load of viable *M.tb* bacteria in a participant's sputum sample. The process starts with RNA isolation from *M.tb* bacteria, followed by RT-qPCR to quantify the RNA, then conversion of the RT-qPCR output (cycle threshold [CT] values) into bacterial load values (estimated colony forming units per millilitre [eCFU/ml]) using a standard curve.

³Culture for storage, MIC and WGS: Isolates will be cultured from sputum samples collected at the screening/enrolment visit using the BD BACTEC MGIT 960 culture system at National Reference TB Laboratory. Cultured isolates will be stored at -80 degrees Celsius for further processing. 70% of clinical isolates will be sent to the study reference laboratory; OSR. OSR will perform quality assurance assessments of the Xpert MTB/XDR cartridge to be tested. The drug patterns of resistant strains detected with the XDR assay will be fully characterized by OSR. In parallel, OSR will populate and develop a catalogue of resistance of the sites, complemented by MIC testing, and seek to identify resistance markers to guide future diagnosis and treatment decisions. WGS testing will be conducted on 70% of total samples from participants with RR-TB and HR-TB enrolled from all sites in cohort 1 and 2, respectively. MIC testing for full phenotypic DST will be prioritized on a subset of 480 samples maximum, including strains with unknown mutation patterns and/or from participants failing the proposed regimen. The accuracy of Xpert MTB/XDR test results for drug resistance prediction will be assessed and quality controlled by WGS analysis. One aliquot of viable isolates from study samples will be referred from sites to OSR, arranging one shipment in year 1 and two shipments per year in the years 2, 3, 4.

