- Cost-effectiveness (cost per person tested and incremental cost per DR-TB participant timely initiated on the resistance pattern-appropriate regimen) and, following from that, optimal placement of Xpert XDR in diagnostic & treatment algorithm (cohort 1 and 2)
- Accuracy of Xpert XDR testing (in comparison with culture + DST/LPA/Next-generation sequencing [NGS]), by type of DR-TB (cohort 1 and 2)
- Operational feasibility of Xpert XDR testing (infrastructure requirements and HR needs) (cohort 1 and 2)
- Quality of Xpert XDR tests (indeterminate rate, DNA contamination rate, and performance variation [in time and between sites]) (cohort 1 and 2)
- Clinical utility and feasibility of TB-MBLA in bacteriological follow-up of DR-TB (in comparison with routine culture), by type of DR-TB and regimen (cohort 1)
- Additional resistance to new and repurposed drugs, by type of DR-TB and regimen (cohort 1 and 2)
- Mathematical modelling of TB-MBLA trajectories in response to treatment

Timing of analysis:

The majority of the above outcomes will be analysed after the end of follow-up, however an interim analysis of the primary study outcomes as well as the safety outcomes is planned for Month 32 (M32) or after complete Month 12 follow-up (M12FU). This will allow for timely informing of policy makers as these new diagnostic tools and regimens are being rolled out.

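### Section 9.2 stratifies Xpert XDR accuracy by DR-TB type, which is defined by the isoniazid and fluoroquinolone results under test, and its stratifier and reference differ from the objective and 7.2

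*Protocol*

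**What the plan says.** The microbiological objective (Table 1, repeated in section 4.4.2) is to assess "performance of the test and triage approach by geographic location using whole genome sequencing (WGS) and Minimum Inhibitory Concentration (MIC) analysis". Section 4.5 lists accuracy and quality of Xpert XDR testing as a secondary outcome in both cohorts.

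Section 7.2, Table 5 note 3, states: "The accuracy of Xpert MTB/XDR test results for drug resistance prediction will be assessed and quality controlled by WGS analysis". WGS is planned on 70% of samples. MIC testing is capped at 480, with priority to unknown mutation patterns and to participants failing the regimen.

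Section 9.2 plans: "Accuracy of Xpert XDR testing (in comparison with culture + DST/LPA/Next-generation sequencing [NGS]), by type of DR-TB (cohort 1 and 2". A later item in the same list plans: "Quality of Xpert XDR tests (indeterminate rate, DNA contamination rate, and performance variation [in time and between sites]) (cohort 1 and 2".

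On where type comes from, section 5 says: "The Xpert MTB/XDR assay will enable prompt identification of the following DR-TB participant categories", and lists HR-TB, rifampicin mono-resistant, MDR and pre-XDR TB. Of the choice of regimen it adds: "This will be guided by the TB resistance pattern categorization from the Xpert MTB/XDR diagnostic".

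Cohort 1 is entered on rifampicin resistance. Cohort 2 is entered (section 6.3) on: "Rifampicin susceptible co-occurring with INH, fluoroquinolone, ethionamide or aminoglycoside resistance (detected by Xpert XDR) occurring alone or in combination".

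**The concern.** The three places that describe the accuracy assessment do not agree. The objective stratifies by location and 9.2 by DR-TB type. The reference is WGS with MIC in the objective, WGS in 7.2, and a list that includes LPA in 9.2.

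The choice of stratifier matters most. DR-TB type is a function of the isoniazid and fluoroquinolone results, so stratifying by it conditions on the index test or on the reference for those drugs. In the strata they define, the two drugs that drive triage would then lack a usable pair of sensitivity and specificity. Cohort 2 adds a selection problem that no stratifier removes: a rifampicin-susceptible patient whose resistance Xpert XDR misses altogether is never enrolled, so such misses cannot be counted.

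**Working it through.** The protocol gives no sample size or precision for accuracy, so there is no stated figure to reproduce.

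**Step 1. Which cells are forced if Xpert XDR assigns type.** Strata follow section 5. Rifampicin mono-resistant is taken as isoniazid-negative and fluoroquinolone-negative with injectables left open, in line with section 3. Pre-XDR is any rifampicin-resistant strain with fluoroquinolone resistance. Entries are sensitivity / specificity.

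| Stratum | Isoniazid | Fluoroquinolone | Injectable |
|---|---|---|---|
| HR-TB | 100% / 0% | not forced | not forced |
| Rif mono | 0% / 100% | 0% / 100% | not forced |
| MDR | 100% / 0% | 0% / 100% | not forced |
| Pre-XDR | not forced | 100% / 0% | not forced |

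Forced cells: 1 + 2 + 2 + 1 = 6 of 12. A simulation of two million records (assumed true sensitivity 0.94, specificity 0.98) reproduced these values exactly and gave about 0.94 / 0.98 in the other six. The forced values do not depend on those assumptions.

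**Step 2. Illustration for isoniazid in cohort 1.** Inputs: n = 880; 78% isoniazid resistance (the global MDR share of RR-TB in section 2.1, used as an assumption); sensitivity 0.94 (the lower end of the range in section 2.3.2); specificity 0.98 (assumed). Pre-XDR is set aside for simplicity.

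- Resistant: 880 × 0.78 = 686. True positives 686 × 0.94 = 645; false negatives 41.
- Susceptible: 880 − 686 = 194. True negatives 194 × 0.98 = 190; false positives 4.
- Xpert-positive (MDR) stratum: sensitivity 645/645 = 100%, specificity 0/4 = 0%.
- Xpert-negative (Rif mono) stratum: sensitivity 0/41 = 0%, specificity 190/190 = 100%.
- Cohort 1 unstratified by type: 645/686 = 94% and 190/194 = 98%.

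If specificity were exactly 100%, as section 2.3.2 reports against sequencing, the MDR-stratum specificity would be 0/0, undefined rather than 0%.

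**Step 3. If the reference assigns type.** Every strain in the MDR stratum is then isoniazid-resistant and none is fluoroquinolone-resistant. Isoniazid sensitivity can be estimated (0.94 in the simulation) but specificity cannot; for fluoroquinolone it is the reverse. The same six cells each lose one measure.

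**Step 4. Cohort 2.** Assumed resistance among rifampicin-susceptible TB: isoniazid 10% (section 9.1), fluoroquinolone 2%, injectable 1%. Drugs are drawn independently and ethionamide is ignored.

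- P(Xpert fluoroquinolone positive) = 0.02 × 0.94 + 0.98 × 0.02 = 0.0384.
- P(Xpert injectable positive) = 0.01 × 0.94 + 0.99 × 0.02 = 0.0292.
- P(neither) = 0.9616 × 0.9708 = 0.9335.
- Apparent isoniazid sensitivity = 0.94 / (1 − 0.06 × 0.9335) = 0.996.
- Apparent isoniazid specificity = 0.98 × (1 − 0.9335) / (1 − 0.98 × 0.9335) = 0.765.

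The simulation agrees (0.996 / 0.76) and gives about 0.99 / 0.87 for fluoroquinolone. With true specificity 0.995 it gives 0.998 / 0.88 for isoniazid. Sensitivity is overstated and specificity understated. Fluoroquinolone and injectables inside the HR-TB stratum kept their true values because the drugs were drawn independently. Shared causes of error, such as low bacillary load, would break that.

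**Step 5. Reference coverage.** WGS at 70% of cohort 1 is 0.70 × 880 = 616, leaving 264 without it. Table 5 lists the Hain assays as routine at screening. The phenotypic DST named in 7.2 is to bedaquiline and linezolid, which Xpert XDR does not test, although section 2.1 describes wider phenotypic testing in routine care. LPA is therefore a likely fallback where WGS is missing.

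**The case against.** The best defence is that 9.2 never says which result defines type. Section 3 defines types by resistance without naming a test, section 2.3.2 says XDR-TB needs further DST to bedaquiline and linezolid, and section 6.2.3 takes type from registers for the historical cohort. This stands: the 0% or 100% values are conditional on Xpert XDR assigning type. It does not rescue the analysis, because reference-assigned type costs one measure in the same six cells.

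A second defence reads type of DR-TB as the target condition, so that accuracy is reported for detecting each type. That would be harmless. Elsewhere in 9.2, however, type is a stratifier (adverse events, TB-MBLA), and the repair is simply to say what this reading would need.

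Third, location is not dropped: the Quality item covers variation between sites, and 9.2 equates location with study site. This stands against any claim that location is absent, but the accuracy item itself still departs from the objective.

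Fourth, DST and NGS are listed beside LPA, and precedence among references is normally left to an analysis plan. This is fair. What remains is that 9.2 names as a reference a test that the objective and 7.2 do not. A reader might also carry over section 2.1's remark that LPAs "are associated with a high indeterminate rate (~30%) in smear-negative patients" as the share lost. That remark follows a statement about testing sputum, while 9.2 may mean LPA on culture, so the figure does not transfer.

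**Conclusion.** The point holds in limited form. Accuracy by DR-TB type gives no usable sensitivity and specificity pair in 6 of 12 drug-by-stratum cells: isoniazid in HR-TB, Rif mono and MDR, and fluoroquinolone in Rif mono, MDR and pre-XDR. This follows from the definitions, whichever test assigns type; only the form of the failure differs. Injectables, fluoroquinolone in HR-TB and isoniazid in pre-XDR are not forced.

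A reader might infer that all the stratified accuracy results are void, that admitting LPA produces the 0% and 100% values, or that the accuracy claim will be too favourable by a known amount. The documents support none of these. Half the cells are unaffected, LPA plays no part in the forced values, and the size of any LPA bias would rest on a rate of resistance missed by both tests that the protocol does not give.

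The cohort 2 problem is firmer, since section 6.3 makes entry depend on the index test. Its direction is clear; the figures in the working rest on assumed prevalences, assumed accuracy and independence between drugs.

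**What to change.** Reword the accuracy item in 9.2 as follows.

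- **Cohort 1:** sensitivity and specificity per drug and by geographic location, not within DR-TB type, with WGS as the reference as in 7.2.
- **MIC and phenotypic DST:** report agreement separately, because the MIC subset (at most 480) is selected.
- **LPA:** report as a comparator test on the same samples, not as a reference.
- **Cohort 2:** report only the proportion of Xpert XDR positives confirmed by WGS (positive predictive value), with no sensitivity or specificity.
- **Location:** state whether it means site or country. Country is the more workable: at 70% WGS coverage, 220 participants give 154, of whom about 154 × 0.22 = 34 would be isoniazid-susceptible on the 78% assumption. The average over 13 sites is 616/13 = 47 participants before any split by resistance.

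The cost is wording only. No extra samples or tests are needed. The accuracy set is limited to the planned 70% with WGS, about 616 in cohort 1.
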